5.4.3.3. Health Care Resource Utilization (HCRU) and Employment Status

Health Care Resource Utilization (HCRU) will be solicited by study personnel while documenting patient responses. Data to be collected include:

- number of hospital emergency room (ER) visits
- number of overnight hospital stays
- number of other visits with healthcare professional
- number of hospital ER visits related to migraine headache
- number of overnight hospital stays related to migraine headache
- number of other visits with healthcare professional related to migraine headache

- number of times admitted to hospital
- number of time admitted to hospital related to migraine

Visits associated with their participation in the clinical trial should not be included in the responses. A question on employment status is also solicited, given the correlation and potential confounding with health outcomes measures.

At the baseline visit, these questions will be asked for the time frame of past 6 months. At postbaseline visits, the questions will be asked for the time from last visit to current visit.

Incidence rates (HCRU events per 100 patient years) will be calculated for different study periods.

HCRU data and employment status will be summarized; change from baseline in incidence rates will be analyzed.

5.4.3.4. Migraine Interictal Burden Scale (MIBS-4)

The Migraine Interictal Burden Scale (MIBS-4) measures the burden related to headache in the time between attacks. The self-administered instrument consists of 4 items that address disruption at work and school, diminished family and social life, difficulty planning, and emotional difficulty. The questionnaire specifically ask about the effect of the disease over the past 4 weeks on days without a headache attack. Response options include: don't know/not applicable (0), never (0), rarely (1), some of the time (2), much of the time (3), or most or all of the time (3). Each response has an associated numerical score, with the summation across all 4 items resulting in a total score ranging from 0 to 12, and the level of interictal burden being categorized into the following: 0 for none, 1-2 mild, 3-4 moderate and ≥5 severe (Buse et al. 2007, 2009).

MIBS-4 is collected at each monthly visit from baseline to the end of the study. The total score will be analyzed. Each item score and the level of interictal burden will be summarized.

5.4.3.5. European Quality of Life 5-Dimensions 5-Levels (EQ-5D-5L)

The European Quality of Life 5-Dimensions 5-Levels (EQ-5D-5L) questionnaire is a widely used, generic patient-rated scale that assesses current health status at the time of questionnaire completion, that is 'today' (The EuroQol Group 1990; Herdman et al. 2011). The questionnaire consists of 2 parts. The first part assesses 5 dimensions (mobility, self-care, usual activities, pain/discomfort, and anxiety/depression) that have 5 possible levels of response (no problems, slight problems, moderate problems, severe problems, extreme problems). Answers to these 5 dimensions define a patient's health state. Given a patient's health state, the patient's country-specific health state index value can be obtained from the country-specific value set.

Country-specific value set is derived from valuation research that aims to measure how health is valued by people in a country. The valuation research includes a representative sample of participants from the general population in that country. In the valuation study participants are asked to value health by reviewing EQ-5D health states. The result from the valuation study is a value set for that country. The value set is essentially a set of weights to each of the levels in

each EQ-5D dimension. A high weight means that people in that country believe that such a score has a high impact on health-related quality of life.

The health state index value is a single value on a scale from less than 0 (where zero is a health state equivalent to death; negative values are valued as worse than dead) to 1 (perfect health), with higher scores indicating better health utility.

The second part of the questionnaire consists of a visual analog scale (VAS) on which the patient rates their perceived health state from 0 (the worst health you can imagine) to 100 (the best health you can imagine).

The response to each question will be summarized. The health state index values (UK population based and US population based index values calculated based on the value sets @https://euroqol.org/wp-content/uploads/2018/02/EQ-5D-5L_Crosswalk_Value_Sets.xls) and VAS score will be analyzed.

5.4.3.6. Work Productivity and Activity Impairment Questionnaire (WPAI)

The Work Productivity and Activity Impairment Questionnaire (WPAI) is a patient-reported instrument developed to measure the impact on work productivity and regular activities attributable to a specific health problem (Reilly et al. 1993); for this study, the questions are specific to migraine. Recall period is the past 7 days. The scale contains 6 items that measure:

- Q1) employment status,
- Q2) hours missed from work due to migraine,
- Q3) hours missed from work for other reasons,
- Q4) hours actually worked,
- Q5) degree migraine affected productivity while working (0-10, 0 –no effect, 10-completely prevent to work), and
- Q6) degree migraine affected productivity in regular unpaid activities (0-10, 0 –no effect, 10-completely prevent me from doing).

Four scores are calculated from the responses to these 6 items as impairment percentages (Reilly et al. 1993), with higher numbers indicating greater impairment and less productivity, i.e., worse outcomes.

- Absenteeism: Percent work time missed due to migraine (%) = Q2/(Q2 + Q4) *100 for those who were currently employed.
- Presenteeism: The Percent Impairment While Working due to migraine (%) = Q5*100/10 for those who were currently employed and actually worked in the past seven days
- The Percent Overall Work Impairment due to migraine (%) = $(Q2/(Q2 + Q4) + (1 Q2/(Q2 + Q4)) \times (Q5/10))*100$ for those who were currently employed;
- Activity Impairment: The Percent Activity Impairment due to migraine (%) = Q6*100/10 for all respondents.

The employment status will be summarized, and the four derived scores will be analyzed.

5.4.4. Safety Endpoints

Safety endpoints consist of the incidences of treatment-emergent adverse events (TEAEs), serious adverse events (SAEs) and discontinuations due to adverse events (DCAEs), vital signs (blood pressure, pulse, and body temperature) and weight, electrocardiograms (ECGs), and laboratory measures (chemistry, hematology and urinalysis).

5.5. Statistical Analyses

5.5.1. General Considerations

Treatment effects will be evaluated based on an overall 2-sided significance level of 0.05 for all efficacy and safety analyses. The 95% confidence intervals (CIs) or standard errors for the difference in least-square means (LSMeans) between treatment groups will be provided.

Any change to the data analysis methods described in the protocol will require an amendment ONLY if it changes a principal feature of the protocol. Any other change to the data analysis methods described in the protocol and the justification for making the changes will be described in the SAP and/or in the clinical study report (CSR).

Statistical analysis of this study will be the responsibility of Eli Lilly and Company or designee. SAS® software will be used to perform most or all statistical analyses.

5.5.1.1. Model Specifications and Adjustment for Covariates

This section specifies the general model terms and adjustment for covariates for different types of variables. For details of analysis methods, please refer to the specific sub-sections under Section 5.5.

Continuous Variables with Repeated Measures

Change from baseline of continuous variables with repeated measures will be analyzed using a mixed model repeated measures (MMRM) analysis. An MMRM analysis refers to a restricted maximum likelihood (REML)-based, mixed-effects repeated measures analysis using all the longitudinal observations at each postbaseline visit.

Unless otherwise specified, the MMRM will include the fixed, categorical effects of treatment, baseline migraine frequency category (low episodic migraine, high episodic migraine, and chronic migraine), pooled country, month, and treatment-by-month interaction, as well as the continuous, fixed covariates of baseline value and baseline value-by-month interaction. The baseline value and baseline-by-month interaction are included to account for the differential influence over time that the baseline value has on the postbaseline values. Rules for pooling countries are defined in Section 5.5.1.3. Pooled country and baseline migraine frequency category will be excluded in MMRM models for safety measures.

Continuous Variables Without Repeated Measures

For continuous variables without repeated measures, the change from baseline to LOCF endpoint will be analyzed using an analysis of variance (ANOVA) or an analysis of covariance (ANCOVA) model.

The ANOVA model for continuous efficacy / health outcome variables will contain the main effects of treatment, baseline migraine frequency category, and pooled country. The ANCOVA model for continuous efficacy / health outcome variables will contain the main effects of treatment, baseline migraine frequency category, pooled country, and appropriate baseline value.

When an ANOVA or ANCOVA model is used to analyze continuous safety variables, baseline migraine frequency category and pooled country will be removed from the model terms.

Unless otherwise specified, when ANOVA model or ANCOVA model is used, type III sum-of-squares for the LSMeans will be used for the statistical comparisons.

Binary Variables with Repeated Measures

Binary variables with repeated measures will be analyzed in generalized linear mixed models (GLIMMIX) as pseudo-likelihood-based mixed effects repeated measures analysis.

The GLIMMIX models for the repeated binary outcomes will include the fixed, categorical effects of treatment, month, baseline migraine frequency category, and treatment-by-month interaction, as well as the continuous, fixed covariate of baseline value. When the fixed covariate of the continuous baseline value is the number of monthly migraine headache days, the baseline migraine frequency category will be excluded. Pooled country and the baseline value-by-month interaction will be excluded from the model in order to increase the likelihood of convergence.

Categorical Variables without Repeated Measures

For categorical efficacy variables without repeated measures, comparisons between treatment groups will be performed using logistic regressions. The logistic model will include the main effect of treatment, baseline migraine frequency category, and appropriate baseline value as a covariate.

For some health outcome variables without repeated measures during the double-blind treatment phase, as the scores of the categories (or number of events in HCRU) do not usually satisfy normal assumption, the change from baseline score will be analyzed using nonparametric tests:

Kruskal–Wallis test (Kruskal and Wallis 1952) for treatment comparison, and Wilcoxon Signed-rank test (Wilcoxon 1945) to compare the change from baseline within each treatment group.

For safety categorical variables and categorical variables of demographics and baseline characteristics, comparisons between treatment groups will be performed using Fisher's exact test as baseline migraine frequency is not expected to have an impact on the safety profile and does not have an impact on baseline measures.

5.5.1.2. Handling of Dropouts or Missing Data

Two statistical approaches to handling missing data will be used as appropriate: repeated measures analyses and ANCOVA/ANOVA model using change from baseline to LOCF endpoint.

For the repeated measures analyses, the model parameters are simultaneously estimated using restricted likelihood estimation incorporating all of the observed data. Estimates have been shown to be unbiased when data are missing at random.

Please refer to Section 5.4.1 for approach to handling missing diary data for derivation of migraine headache days and other efficacy measures (with the exception of migraine attacks) derived from ePRO data per 30-day period.

Approaches to handling missing diary data for the derivation of migraine attack

For the derivation of the number of monthly migraine attacks, the LOCF method will be used to impute the missing ePRO diary days. If the patient was migraine headache-free on the day before the missing ePRO diary day, this would be carried forward as no migraine headache day until the actual next non-missing diary day. On the other hand, if the day before the missing ePRO diary day is a migraine headache day, then it would be carried forward as migraine headache day until the next non-missing diary day. The imputation will be carried out for all the missing diary days between the first non-missing to the last day.

If the diary compliance rate for a monthly interval is \leq 50%, the number of monthly migraine attacks during that month will be considered missing. Please refer to Section 5.5.7 for diary compliance rate calculation.

5.5.1.3. Rules for Pooling Countries

All countries with fewer than 4 randomized patients in the placebo group or fewer than 4 randomized patients in the galcanezumab group with baseline and at least 1 postbaseline migraine headache day value will be pooled within region (North America, Europe, and Asia, as defined in Table CGAW.5.8) and considered as a single country for analyses.

All analyses will use pooled country when applicable. The investigative site numbers will be included in the listings.

5.5.1.4. Analysis Populations

There are 5 analysis populations defined:

Intent-to-treat (ITT) population: All patients who are randomized and receive at least 1 dose of study drug.

ITT episodic sub-population: All patients with episodic migraine who are randomized and receive at least 1 dose of study drug.

Safety population: This population is the same as the ITT population defined above.

GMB-treated population: All patients who have exposure to galcanezumab (GMB). The GMB-treated population will be used for summaries for GMB-treated time.

GMB-treated time is the period during which a patient received GMB.

- For patients who receive GMB in the double-blind treatment period (SP III) only, GMB-treated time begins and ends in SP III.
- For patients who receive GMB in both treatment periods, GMB-treated time begins in SP III and extends through SP IV.
- For patients who receive placebo in the double-blind treatment period, GMB-treated time begins in SP IV.

Open-label treatment population: All patients who enter the open-label treatment phase as indicated by receiving any injections starting from Visit 6. Analyses for open-label phase only will be based on the open-label treatment population.

Unless otherwise stated, all analyses will be conducted according to the ITT principle on the ITT population. That is, patients will be analyzed according to the treatment to which they were randomized, regardless of whether they actually received a different treatment.

Safety analyses and summary for exposure for the double-blind treatment phase will be conducted based on the modal treatment patients have received (placebo or GMB) during the double-blind treatment phase from the first dose at Visit 3 to the last dose at Visit 5. For determining modal dose:

- A dosing visit contributes to placebo if a patient receives no injections other than placebo. Otherwise, the dosing visit contributes to GMB in the modal dose calculation.
- Modal dose is the most frequent dose. If there is a tie, GMB will be used.

Safety and exposure data for GMB-treated time will be summarized.

5.5.1.5. Baseline and Postbaseline Definition

Table CGAW.5.4 describes the rules for determining the patient population and baseline and postbaseline observations for each study phase and type of analysis. When "last of Visit x-x" is used in the table, the last non-missing observation obtained in the visit interval will be used.

Table CGAW.5.4. Patient Population with Baseline and Postbaseline Definitions by Study Period and Type of Analysis

Study Period/Analysis	Patient Population	Baseline Observation	Postbaseline Observation(s)		
Study Period III					
Efficacy analyses (Repeated measures) or average of observed monthly values		Visit 3	All scheduled visits 3 < Visits ≤6		
Efficacy analyses at LOCF endpoint	ITT population and ITT episodic sub-population	Visit 3	Last of Visit 3.01–6		
Health outcome analyses (Repeated measures)	with a baseline and at least 1 postbaseline observation	Visit 3	All scheduled visits 3 < Visits ≤6		
Health outcome analyses at LOCF endpoint or for average of observed monthly values		Visit 3	Last of Visit 3.01-6		
Treatment-emergent adverse events	Safety population	All Visits 1–3*a	All Visits 3.01–6		
Serious adverse events, discontinuations due to adverse events	Safety population	NA	All Visits 3.01–6		
Treatment-emergent abnormal laboratory values	Safety population with normal (with respect to direction being analyzed) laboratory values at all non-missing baseline visits and who have at least 1 postbaseline observation	Low: Min of Visits 1–3 High: Max of Visits 1–3 Abnormal: All Visits 1–3	Low: Min of Visits 3.01–6 High: Max of Visits 3.01–6 Abnormal: All Visits 3.01–6		
Treatment-emergent changes in temperature and weight	Safety population with a baseline and at least 1 postbaseline observation	Low: Min of Visits 1–3 High: Max of Visits 1–3	Low: Min of Visits 3.01–6 High: Max of Visits 3.01–6		
Treatment-emergent changes in blood pressures, pulse, and ECGs	Safety population with a baseline and at least 1 postbaseline observation	Low: Last of Visits 1–3 High: Last of Visits 1–3	Low: Min of Visits 3.01–6 High: Max of Visits 3.01–6		
Continuous safety analyses (Repeated Measures)	Safety population with a baseline and at least 1 postbaseline observation	Last of Visits 1–3	All scheduled visits 3 < Visits ≤6		
Continuous safety analyses – change from baseline to LOCF endpoint (ANCOVA)	Safety population with a baseline and at least 1 postbaseline observation	Last of Visits 1–3	Last of Visits 3.01–6		

Patient Population with Baseline and Postbaseline Definitions by Study Period and Type of Analysis

Study Period/Analysis	Patient Population	Baseline Observation	Postbaseline Observation(s)
Study Period IV			
Logistic regression – patients maintained 50% response	ITT population – GMB-treated in double-blind study phase	Visit 3	All scheduled visits 6 < Visits ≤9
Treatment-emergent adverse events by preferred term	Open-label treatment population	All Visits 1–6*a	All Visits 6.01–9
Study Periods III/IV Combined			
Efficacy/health outcome analyses	ITT population and ITT episodic sub-population with a baseline and at least 1 postbaseline observation	Visit 3	All scheduled visits 3 < Visits ≤9
Continuous safety analyses (Repeated Measures)	Safety population with a baseline and at least 1 postbaseline observation	Last of Visits 1–3	All scheduled visits 3 < Visits ≤9
GMB-Treated Time			
Treatment-emergent adverse events	GMB-treated population	All Visits 1–3 before double-blind phase dosing for patients treated with GMB during SP III; All Visits 1–6 before open-label phase dosing for patients treated with placebo during SP III*a	All visits after first dosing of GMB through Visit 9
Serious adverse events, discontinuations due to adverse events	GMB-treated population	NA	All visits after first dosing of GMB through Visit 9
Treatment-emergent abnormal laboratory values	GMB-treated population with normal (with respect to direction being analyzed) laboratory values at all non-missing baseline visits and who have at least 1 postbaseline observation	Visits 1–3 before double-blind phase dosing for patients treated with GMB during SP III; Visits 1–6 before open-label phase dosing for patients treated with placebo during SP III	All visits after first dosing of GMB through Visit 9: Visits 3.01–9 for GMB-treated patients during SP III; Visits 6.01–9 for placebo-treated patients during SP III

Patient Population with Baseline and Postbaseline Definitions by Study Period and Type of Analysis

			Postbaseline
Study Period/Analysis	Patient Population	Baseline Observation	Observation(s)
GMB-Treated Time			
Treatment-emergent changes in temperature	GMB-treated population with a baseline and at	Min/max of Visits 1–3	Min/max of all visits after
and weight	least 1 postbaseline observation	before double-blind phase	first dose of GMB
		dosing for patients treated	through Visit 9 for
		with GMB during SP III	low/high, respectively:
I		for low/high, respectively;	Visits 3.01–9 for
		Min/max of Visits 1–6	GMB-treated patients
		before open-label phase	during SP III; Visits 6.01–
		dosing for patients treated	9 for placebo-treated
		with placebo during SP III	patients during SP III.
		for low/high, respectively	
Treatment-emergent changes in blood pressure,	GMB-treated population with a baseline and at	Last non-missing value	Min/max of all visits after
pulse, and ECGs	least 1 postbaseline observation	from Visits 1–3 before	first dosing of GMB
		double-blind phase dosing	through Visit 9 for
		for patients treated with	low/high, respectively:
		GMB during SP III;	Visits 3.01–9 for
		Last non-missing value	GMB-treated patients
		from Visits 1–6 before	during SP III; Visits 6.01–
		open-label phase dosing	9 for placebo-treated
		for patients treated with	patients during SP III.
		placebo during SP III.	

Abbreviations: AE = adverse event; ANCOVA = analysis of covariance; ECG = electrocardiogram; GMB = galcanezumab; ITT = intent-to-treat; LOCF = last observation carried forward; max = maximum; min = minimum; NA = not applicable; SP = study period.

^{*}a, AEs that occurred on the visit date of Visit 3 or Visit 6 will be determined to be predose or after dose based on AE start time and the injection time: predose if AE start time is before the injection time and post dose if AE start time is after the injection time. Note: Visit 3.01 indicates the first unscheduled visit occurring after Visit 3 and prior to Visit 4. Visit 6.01 indicates the first unscheduled visit occurring after Visit 6 and prior to Visit 7.

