3.3. Benefit/Risk Assessment

Galcanezumab is a humanized monoclonal antibody that potently and selectively binds to CGRP and prevents its biological activity without blocking the CGRP receptor. The efficacy of galcanezumab for the prevention of migraine has been demonstrated in three Phase 3 randomized, double-blind trials which found statistically significant and clinically meaningful mean reduction of monthly migraine headache days and improvement in patient function compared to placebo in patients with episodic and chronic migraine. Across Phase 2 and Phase 3 clinical studies in patients with migraine, galcanezumab exhibited a favorable safety profile at doses up to 300 mg every 4 weeks for 3 months, or 240 mg monthly for up to 1 year. The incidences of serious adverse events (SAEs) and discontinuations due to adverse events (AEs) were low, and treatment-emergent adverse events (TEAEs) were generally of mild to moderate severity. In the Phase 3 studies, the most commonly reported TEAEs were injection site pain and injection site reactions, also generally of mild to moderate severity. There was no evidence of an effect on cardiovascular function. These data provide a favorable benefit-risk profile for galcanezumab for migraine prevention.

More information about the known and expected benefits, risks, SAEs, and reasonably anticipated AEs of galcanezumab are to be found in the Investigator's Brochure (IB).

4. Objectives and Endpoints

Table CGAW.2 shows the objectives and endpoints of the study. Table CGAW.3 provides migraine and headache endpoint definitions.

Table CGAW.2. Objectives and Endpoints

Objectives	Endpoints					
Primary Objective To test the hypothesis that galcanezumab is superior to placebo in the prevention of migraine in patients with treatment-resistant migraine	The overall mean change from baseline in the number of monthly migraine headache days during the 3-month double-blind treatment phase in the total population (episodic and chronic migraine) ^a					
Key Secondary Objectives Note: All key secondary objectives will be tested in both the total population (episodic and chronic migraine) and the episodic migraine subpopulation unless otherwise specified.	The specific methodology (including testing order and population) for the tests of the following key secondary endpoints will be specified in Section 10.3.3.2 and the statistical analysis plan:					

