5.5.12.1.1. Adverse Events

TEAEs are defined as the reported AEs that first occurred or worsened during the postbaseline phase compared with baseline phase. For each TEAE, the severity level of the event (mild, moderate, or severe) will be determined by patient or physician opinion. The MedDRA Lowest Level Term (LLT) will be used in the treatment-emergent computation. For each LLT, the maximum severity at baseline will be used as the baseline severity. If the maximum severity during postbaseline is greater than the maximum baseline severity, the event is considered to be treatment-emergent for the specific postbaseline period.

For each patient and TEAE, the maximum severity for the MedDRA level being displayed (PT, High Level Term, or SOC) is the maximum postbaseline severity observed from all associated LLTs mapping to that MedDRA level.

For events that are sex-specific, the denominator and computation of the percentage will include only patients from the specific gender.

5.5.12.1.1.1. Potential Hypersensitivity Events

Potential hypersensitivity events (immediate and non-immediate) will be identified from a search of preferred terms generated from the following queries:

- Anaphylactic reaction (SMO 20000021)
- Broad and narrow terms in the Angioedema (SMQ 20000024)
- Broad and narrow terms in the Hypersensitivity (SMQ 20000214)

A listing of patients who reported an AE (TEAEs with all visits 1-3 as baseline, SAEs, and DCAEs) identified from these analyses will be medically reviewed to determine if the terms identified represent actual hypersensitivity events. Listings should include information on timing of event relative to latest dose of study drug administration, the event term from this query, other AEs for the patient and timing, any abnormal laboratory findings, and medical history. Only those that are judged medically to be hypersensitivity events will be included in the final tables.

The number and percentage of patients with TEAEs, SAEs, and AEs resulting in study drug discontinuation will be summarized by treatment groups using MedDRA PT nested within the SMQ. Events will be ordered by decreasing frequency within the SMQ.

The number and percentage of patients with treatment-emergent (TE) hypersensitivity events by maximum severity will be summarized by treatment groups using MedDRA PT.

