The number and percentage of patients with TE hypersensitivity events by timing will be summarized using MedDRA PT. Events will be ordered by decreasing frequency. Note the timing of the hypersensitivity events is collected through eCRF and categorized into the following 4 categories:

- Immediate occurs within minutes (<60 minutes) from study drug administration.
- Acute Reaction occurs from 1 up to 6 hours from study drug administration.
- Delayed Reaction occurs from >6 hours through 14 days from study drug administration, which will be split into 2 categories: on the same day of injection and after the day of injection.
- Reaction >14 days from study drug administration.

5.5.12.1.1.2. Adverse Events Related to Injection Sites

Adverse events related to injection sites will be defined using terms from the MedDRA High Level Term "Injection Site Reactions".

The number and percentage of patients with TEAEs related to injection sites, SAEs related to injection sites, and AEs related to injection sites resulting in study drug discontinuation will be summarized using MedDRA PT. Events will be ordered by decreasing frequency.

The number and percentage of patients with TEAEs related to injection sites by maximum severity will be summarized by treatment groups using MedDRA PT.

The number and percentage of patients with TEAEs related to injection sites by timing will be summarized using MedDRA preferred terms ordered by decreasing frequency. Note the timing of AEs related to injection sites is collected through eCRF and categorized into the same categories as for hypersensitivity events.

Adverse events related to injection sites will be summarized by whether comfort measures are used and what comfort measures are used.

Follow-up forms for adverse events related to injection sites will be summarized as well.

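### In the galcanezumab-treated-time tables, a former placebo patient's injection-site reaction is not counted if the same term occurred at equal or greater severity on placebo, so the pooled percentage can only err downward

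*SAP*

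**What the plan says.** SAP 5.5.1.5, Table CGAW.5.4, defines baseline and postbaseline for treatment-emergent adverse events (TEAEs) in galcanezumab-treated time. The postbaseline window is the same for everyone: "All visits after first dosing of GMB through Visit 9". The baseline depends on the treatment given in Study Period III (SP III):

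- Galcanezumab in SP III: "All Visits 1–3 before double-blind phase dosing for patients treated with GMB during SP III".
- Placebo in SP III: "All Visits 1–6 before open-label phase dosing for patients treated with placebo during SP III".

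SAP 5.5.12.1.1 gives the counting rule. Baseline severity is set term by term: "For each LLT, the maximum severity at baseline will be used as the baseline severity". Emergence then needs a strict increase: "If the maximum severity during postbaseline is greater than the maximum baseline severity, the event is considered to be treatment-emergent".

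SAP 5.5.12 makes Table CGAW.5.4 the default for all safety measures unless another baseline is named. The injection-site section (SAP 5.5.12.1.1.2) names none. It plans, among others, this table: "The number and percentage of patients with TEAEs related to injection sites by maximum severity will be summarized by treatment groups using MedDRA PT".

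Protocol 5.1 states that placebo patients receive two injections at the first dosing visit and one at each of the next two. Protocol 3.3 says of the Phase 3 studies that "the most commonly reported TEAEs were injection site pain and injection site reactions".

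**The concern.** Each injection is a new exposure, and a local reaction to one can recur with the next. A reaction after a placebo syringe says little about whether the patient will react to a later galcanezumab syringe. The rule nevertheless lets the first cancel the second when the term is the same and the severity is no greater. This happens only in former placebo patients, because only their baseline contains injections. The first exposure affected is their two-injection loading dose at Visit 6.

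The SAP revision history says the galcanezumab-treated-time analysis replaced the separate open-label safety analyses and is meant to give overall estimates that do not depend on study phase. For injection-site events, phase history does decide whether a reaction is counted. At stake is the descriptive rate of the kind of event that Protocol 3.3 names as most common. A lower rate in former placebo patients could also be misread as better tolerability.

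**Working it through.** **Step 1. The two baselines.** Visit intervals come from the Schedule of Activities (Protocol Section 2).

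- Visits 1 to 3: (3 to 30) + (30 to 45) = 33 to 75 days, with no injections.
- Visits 1 to 6: add three intervals of 28 to 32 days, that is 84 to 96 days. The total is 117 to 171 days. This includes dosing at Visits 3, 4 and 5, with 2 + 1 + 1 = 4 placebo injections.

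**Step 2. Apply the severity rule** to one injection-site Lowest Level Term in a former placebo patient.

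| Worst on placebo | Mild on galcanezumab | Moderate | Severe |
|---|---|---|---|
| None | counted | counted | counted |
| Mild | not counted | counted | counted |
| Moderate | not counted | not counted | counted |
| Severe | not counted | not counted | not counted |

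A patient on galcanezumab from SP III has had no study injection before baseline ends, so in effect always falls in the first row.

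**Step 3. Direction.** The maximum severity over Visits 1 to 6 is at least the maximum over Visits 1 to 3. The longer baseline can remove events from the count and cannot add any. The sign of the bias needs no assumption.

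**Step 4. Illustration of size.** The plan states no figure to reproduce, and the documents give no injection-site incidence. The assumptions are:

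- 420 patients randomised 1:1 (SAP 5.2), all dosed, so 210 are on galcanezumab from SP III.
- 10% discontinuation (SAP 5.2), with all remaining placebo patients entering the open-label phase: 210 × 0.9 = 189. The pooled table then holds 210 + 189 = 399 patients, of whom 189/399 = 47% are former placebo patients.
- The same true incidence r in both groups, and a share m of former placebo patients' cases masked.

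Observed pooled incidence = [210r + 189r(1 − m)] / 399. Relative understatement = m × 189/399, whatever the value of r.

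| m | Relative understatement | Pooled percentage if r = 10% | Patients not counted if r = 10% (189 × 0.10 × m) |
|---|---|---|---|
| 10% | 4.7% | 9.5% | 1.9 |
| 25% | 11.8% | 8.8% | 4.7 |
| 50% | 23.7% | 7.6% | 9.5 |

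The values of m are arbitrary. The table shows how masking passes through to the pooled percentage, not how much masking to expect. For a total of patients with any injection-site event, these losses are upper bounds: a patient whose pain is masked but who has new erythema, a different term, still counts.

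**The case against.** The strongest reply is that the rule is deliberate. Protocol 10.3.4.1 sets the baseline for each study period as all visits through the last scheduled visit of the prior period, and Protocol Appendix 1 defines a TEAE against the pretreatment state. For a former placebo patient, everything before the first galcanezumab dose is Visits 1 to 6. Both groups are thus measured against their own time before galcanezumab, which is one principle applied to two histories. This stands, and the plan does not contradict itself here. It does not remove the effect, because for injection-site events that principle gives one group a baseline with injections and the other a baseline without them.

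The second reply is that other outputs are intact. This also stands. Serious adverse events and discontinuations due to adverse events have no baseline condition in Table CGAW.5.4. The randomised SP III comparison uses Visits 1 to 3 in both arms and supplies the controlled estimate. The galcanezumab-treated-time tables are descriptive only (SAP 5.5.12.1). The summaries by comfort measure and of the follow-up forms are not expressly limited to TEAEs, though neither is the incidence table at issue.

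A reader might infer that the SAP is inconsistent because the hypersensitivity listing uses its own baseline ("TEAEs with all visits 1-3 as baseline, SAEs, and DCAEs"). The documents do not support that. SAP 5.5.12 allows exceptions to the default, and this one applies to a listing for medical review.

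A reader might also want Visits 1 to 3 as baseline for all TEAEs, or a new baseline for the separate Study Period IV (SP IV) table. The argument does not reach that far. An intermittent event that resolved on placebo and later recurred would be newly labelled as galcanezumab-emergent, and the SP IV table reasonably asks what is new in that period.

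**Conclusion.** The point holds for injection-site TEAEs in galcanezumab-treated time. Same-term reactions of equal or lower severity are dropped in former placebo patients and kept in patients on galcanezumab from SP III. The pooled percentage therefore mixes two effective definitions and can only be too low. That conclusion rests on the text alone.

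The size is not known. The range of 4.7% to 23.7% in relative terms rests on assumed masking shares of 10% to 50%, equal true incidence in both groups, and full entry of the remaining placebo patients into the open-label phase.

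A reader might infer a much larger loss. Suppose 15% of patients react on placebo, 70% of them repeat the same term on galcanezumab, and 80% of those do so at no greater severity. Then 0.15 × 0.70 × 0.80 = 8.4 points are lost, which is 56% of an assumed true incidence of 15%. None of these inputs is in the documents, and together they are strained: they imply an incidence on galcanezumab of only (15 − 10.5)/85 = 5.3% among patients with no placebo reaction. No large loss is demonstrated.

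No efficacy result, randomised safety comparison, serious-event count or discontinuation count changes. This is a cheap improvement to a descriptive table.

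**What to change.** In SAP 5.5.12.1.1.2 and Table CGAW.5.4, add a rule for injection-site events in galcanezumab-treated time only. Count every event with onset after the patient's first galcanezumab dose, whatever reactions occurred on placebo. Use the adverse event start time and injection time that the footnote to Table CGAW.5.4 already relies on for Visits 3 and 6. Show the result by former SP III treatment as well as pooled. Keep the Visits 1 to 6 baseline for general TEAEs and for the SP IV table, and leave the SP III comparison as it is.

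The cost is minor reprogramming and a short justification for departing from the general severity rule, which Protocol 10.3.1 and SAP 5.5.1 ask for when methods change. The galcanezumab percentage will be slightly higher, and some counted events will resemble reactions the patient also had on placebo. No new data are needed.
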